### 12.3 Hypertension treatment

It can be expected that the included study population will be heterogeneous at baseline in terms of antihypertensive treatment, as this may reflect different individual and local treatment considerations. Antihypertensive treatment prior to inclusion, especially ACE or ARB treatment, should be continued unchanged during “run-in” period and throughout the study if possible.

**Definition:** Hypertension, for the purpose of this study, is defined as systolic pressure >130 mm HG and/or diastolic pressure >80 mm Hg.

All patients should be treated according to local guidelines. In any case the care team should be encouraged to initiate or intensify treatment in case of repeated (or confirmed) blood pressure > 140 mm Hg systolic and or diastolic > 90 mmHg. If local guidelines do not recommend a specific first line antihypertensive agent it is suggested to start with a calcium channel blocker or thiazide diuretic to reduce interference with UACR.

In any case, choice of therapy is left to the discretion of the investigator. RAS blocking agents are accepted, if indicated. If blood pressure cannot be managed consideration of a secondary cause should be studied. If patients are assigned to IMP is started on ACE, ARB or renin-inhibitors the investigator is advised to measure potassium according to local guidelines, to minimize the risk of hyperkalemia.

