3.2 Randomization

At baseline eligible patients with a high-risk proteomics pattern will be included in the intervention part of the study. Randomization lists will be prepared by an independent statistician at the Robertson Centre, University of Glasgow, who is not involved into other tasks of the trial.

The patients will be randomly assigned in a 1:1 ratio to one of the two treatment arms using a block randomization stratified by study center.

Patients will be stratified in the two treatment arms (1:1) based on whether or not the patients is treated with RAS blocking agents at the time of entry (Screening) in order to have the number on RAS blocking agents balanced in the two treatment arms.

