6.3 Analysis methods

6.3.1 Observational study (Observational cohort)

6.3.1.1 Primary analysis of primary endpoint

In the observation cohort a comparison between the high- and low-risk stratum will be conducted using an unadjusted Cox-regression model with log-rank test.

In addition, adjustment for age, gender, Hba1c, systolic blood pressure, retinopathy eGFR and UACR at baseline will be conducted.

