6.3.2 Intervention study (Intention to treat cohort)

6.3.2.1 Primary analysis of primary endpoint

In the intention to treat cohort, a comparison between active and placebo treatment will be performed in a Cox-regression model including data on the primary outcome. Adjustments in the model will only be performed for eGFR and/or UACR in the case of a significant unbalance in the baseline value (significance level for unbalance between treatment allocation groups is a p-value < 0.01).

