6.3.2.2 Analysis of secondary endpoints

Based on a 2x2 table included the primary endpoint (event/ event free) vs. treatment allocation (active/ placebo) we will calculate numbers needed to treat and tested for significance using Chi-square test.

For Cox-regression models both unadjusted and adjusted using treatment allocation as determinant. Adjustment for age, gender, HbA_{1c}, systolic blood pressure, retinopathy, study site, eGFR and UACR at baseline will be conducted for both primary and secondary endpoints (see section 6.1.1 and 6.1.2, excluding 6.1.2 C, H and J).

For further clarification of the added value for discrimination, the rIDI will be calculated for all above described Cox-regression models with a significant HR for treatment allocation in the unadjusted model for each endpoint.

For safety outcome (section 6.2.1 J) only AE/SAE with the term hypotension, hyperkalaemia or gynaecomastia will be analysed using chi-square test.

To evaluate changes in UACR and eGFR over time (outcome measurement C and H in section 6.2.1) a linear mix model will be applied with adjustment for eGFR and UACR at baseline.

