6.3.2.3 Sensitivity analysis

In a forest plot each baseline continuous variable: Age, HbA_{1c}, systolic blood pressure, eGFR and UACR will be divided based on the median value and tested for heterogeneity between treatment allocation. Of the categorical variables we will evaluate the effect of: Gender, and presence of retinopathy at baseline also in a forest plot. We expect the largest effect of active treatment in participants with known risk factors of overt kidney disease (high age, HbA_{1c}, systolic blood pressure, UACR and low eGFR, male gender and presence of retinopathy).

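### RAS-blocker use at screening is a randomisation stratum, but no treatment model and no row of the treatment forest plot uses it

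*SAP*

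**What the plan says.** Protocol 8.2 and SAP 3.2 name two stratification factors. Allocation is made "using a block randomization stratified by study center", and patients are also stratified "based on whether or not the patients is treated with RAS blocking agents at the time of entry (Screening) in order to have" similar numbers of users in each arm.

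The protocol treats the start of a RAS blocker as something that can disturb the endpoint measure. Where local guidelines name no first-line agent, Protocol 12.3 says "it is suggested to start with a calcium channel blocker or thiazide diuretic to reduce interference with UACR". Protocol 12.4 asks that patients not on an ACE inhibitor or ARB at screening stay off them until the primary endpoint is reached.

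The treatment analyses in the SAP are:

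- **Primary Cox model (6.3.2.1):** unadjusted by default. "Adjustments in the model will only be performed for eGFR and/or UACR in the case of a significant unbalance in the baseline value", with imbalance judged at p < 0.01.
- **Adjusted Cox models (6.3.2.2):** "Adjustment for age, gender, HbA_{1c}, systolic blood pressure, retinopathy, study site, eGFR and UACR at baseline will be conducted". Study site, the other stratum, is included; RAS use is not.
- **Per-protocol Cox models (6.4):** seven covariates, with neither RAS use nor site.
- **Forest plot (6.3.2.3):** age, HbA1c, systolic pressure, eGFR and UACR split at the median. Then: "Of the categorical variables we will evaluate the effect of: Gender, and presence of retinopathy at baseline also in a forest plot".

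The nearest provisions elsewhere are these:

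- Protocol 15.6 adjusts for significant changes in RAAS blockade during the study, and for baseline demographic variables that differ significantly between groups and relate to albuminuria. The SAP carries neither forward.
- SAP 6.3.1.3 lists use of antihypertensive agents for a chi-square test, in the observational study only.
- SAP 5.5 tabulates antihypertensives by substance group at baseline.

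**The concern.** A factor is normally made a randomisation stratum because it is thought to predict outcome, and the analysis should then condition on it. If it does not, two things follow. First, balance forced by design removes variation that the unstratified test still counts as noise. The test becomes conservative and the hazard ratio is pulled towards 1, to a degree that depends on how prognostic the factor is. Second, spironolactone is tested on top of standard treatment (Protocol 3), so the effect with and without a background RAS blocker is a natural question, and no planned estimate addresses it. Protocol 15.5 classes anything not in the protocol or SAP as exploratory or post hoc, so an estimate added later would have that status.

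**Working it through.** **Inputs from the documents.** Event proportions 40% (placebo) and 24% (spironolactone), 1:1 allocation, 129 per arm (Protocol 15.1, SAP 3.4); two-sided alpha 0.05 (Protocol 15.6, SAP 4.1); power 80%, which the plan writes as beta = 0.80.

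**The plan's own figure.** Unpooled two-proportion formula:

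n = (1.960 + 0.842)² × (0.40×0.60 + 0.24×0.76) / 0.16² = 129.5 per arm, which matches the stated 129.

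**Translation to the Cox analysis.** With proportional hazards, HR = ln(1−0.24)/ln(1−0.40) = 0.537. Expected events at 129 per arm = 129 × (0.40+0.24) = 82.6. Schoenfeld's formula asks for 82 events, and power at 82.6 events is 0.806.

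**Cost of ignoring the stratum.** The documents give neither the share of RAS users nor their hazard ratio against non-users, so both are assumed. Each trial had 258 patients, exact treatment balance within RAS stratum, exponential event times, common follow-up, placebo risk fixed at 40% and a within-stratum treatment HR of 0.537 (1 for type I error). The log-rank score test, which is the Cox score test, was applied unstratified and stratified by RAS use. There were 6,000 runs per scenario; Monte Carlo SE is about 0.005 for power and 0.003 for type I error.

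| RAS share | HR, users vs non-users | Power unstratified → stratified | Type I error unstratified → stratified |
|---|---|---|---|
| 50% | 1 | 0.798 → 0.797 | 0.053 → 0.052 |
| 50% | 0.5 | 0.787 → 0.801 | 0.042 → 0.048 |
| 50% | 2 | 0.786 → 0.797 | 0.047 → 0.054 |
| 50% | 3 | 0.772 → 0.799 | 0.034 → 0.048 |
| 50% | 4 | 0.758 → 0.806 | 0.027 → 0.047 |
| 70% | 1 | 0.789 → 0.788 | 0.046 → 0.045 |
| 70% | 0.5 | 0.786 → 0.799 | 0.052 → 0.057 |
| 70% | 2 | 0.789 → 0.798 | 0.049 → 0.053 |
| 70% | 3 | 0.779 → 0.799 | 0.042 → 0.050 |
| 70% | 4 | 0.777 → 0.803 | 0.039 → 0.049 |

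The loss is therefore about 1 point at a stratum HR of 0.5 or 2, about 2 to 3 points at 3, about 3 to 5 points at 4, and nil at 1.

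**What a forest-plot row could show.** For RAS share p and E events, the SE of the log ratio of HRs is √(4/(Ep) + 4/(E(1−p))). With E = 82.6:

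- p = 0.5: SE = 0.440; ratio detectable with 80% power = exp(2.80 × 0.440) = 3.4.
- p = 0.7: SE = 0.480; ratio = exp(2.80 × 0.480) = 3.8.

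**Why not stratify by centre as well.** SAP 5.3.3 gives 15 sites. Crossed with RAS use that makes 30 cells, or about 82.6/30 = 2.8 events per cell.

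**The case against.** **The gain is small at moderate strengths.** A visible loss needs a 3- to 4-fold stratum effect, and nothing in the documents supports one. This stands, and it sets the size of the point.

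**The protocol's concern is with starting RAS blockers.** Protocol 12.3 wants existing treatment kept unchanged if possible, so run-in UACR is measured on it, and one route to the endpoint is a rise from that run-in value. Stable use is thus partly built into the reference. This stands as a reason to expect a modest prognostic effect. It also means the documents do not support calling RAS blockade the main background influence on UACR. Baseline UACR and systolic pressure, which might absorb part of the effect, are in the adjusted models, but the primary model takes UACR only after an imbalance.

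**Protocol 15.6 may already cover it.** The demographic-variable clause could be stretched to RAS use, but it does not name it, would rarely be triggered by a factor balanced by design, and is absent from the SAP. The other clause concerns change after randomisation.

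**Stronger readings that a reader might infer:**

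- *That the omission invalidates the test.* It does not: the unstratified type I error stays near or below 0.05.
- *That stratifying lifts power well above 80%.* If both marginal rates are held at 40% and 24%, simulated power rises from 82.7% to 85.2% at a stratum HR of 3, and from 80.6% to 85.3% at 4. The 85% level arises because fixing the marginal rates strengthens the within-stratum HR to 0.519 and 0.510. With the HR held at 0.537, stratified power stays at about 80%.
- *That the CKD273 hazard ratio is confounded.* RAS use is indeed not balanced between risk groups, and the adjusted model lacks it ("In addition, adjustment for age, gender, Hba1c, systolic blood pressure, retinopathy eGFR and UACR at baseline will be conducted"). But if one assumes 75% use in high-risk and 55% in low-risk patients, the bias factor (0.75h + 0.25)/(0.55h + 0.45) runs from 0.90 at h = 0.6 to 1.13 at h = 2. The direction is unknown and the prevalences are invented. The planned rates, (40%+24%)/2 = 32% against 8.5%, imply an HR of ln(0.68)/ln(0.915) = 4.3, so such a shift would not change the conclusion. The objective there is also prediction, not a causal effect.

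**Conclusion.** The point holds as a mismatch between randomisation and analysis in the treatment comparison, with a modest consequence: no false-positive risk, and a power loss of about 1 point at a 2-fold stratum effect in either direction, rising to 3 to 5 points at 4-fold. These figures rest on an assumed RAS share of 50% or 70%, an assumed stratum hazard ratio, exact balance within strata and 258 evaluable patients. The plan also lacks any pre-specified estimate of the spironolactone effect by background RAS use. With about 83 events such an estimate can only be descriptive; it would not settle effect modification. Confounding of the CKD273 comparison cannot be established from the documents.

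**What to change.** - **SAP 6.3.2.1:** stratify the primary treatment Cox model by RAS-blocker use at screening, as entered for randomisation.
- **SAP 6.3.2.2 and the per-protocol models in 6.4:** apply the same stratification. Study centre, also absent from the primary model, can stay as the site covariate in 6.3.2.2.
- **SAP 6.3.2.3:** add a RAS blocker yes/no row to the forest plot, labelled descriptive, and state that the interaction has 80% power only for a ratio of hazard ratios of about 3.4 to 3.8.
- **Optional:** add baseline RAS-blocker use to the adjusted CKD273 models as a sensitivity analysis.

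The cost is one extra model term and one subgroup row. ACE inhibitor and ARB use is already recorded at screening (Protocol Table 1, footnote 9), and the stratum is needed at randomisation, so no new data are required. In the simulations stratifying cost no measurable power when RAS use was not prognostic. The change should be made before unblinding.

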6.3.2.2 Analysis of secondary endpoints

Based on a 2x2 table included the primary endpoint (event/ event free) vs. treatment allocation (active/ placebo) we will calculate numbers needed to treat and tested for significance using Chi-square test.

For Cox-regression models both unadjusted and adjusted using treatment allocation as determinant. Adjustment for age, gender, HbA_{1c}, systolic blood pressure, retinopathy, study site, eGFR and UACR at baseline will be conducted for both primary and secondary endpoints (see section 6.1.1 and 6.1.2, excluding 6.1.2 C, H and J).

For further clarification of the added value for discrimination, the rIDI will be calculated for all above described Cox-regression models with a significant HR for treatment allocation in the unadjusted model for each endpoint.

For safety outcome (section 6.2.1 J) only AE/SAE with the term hypotension, hyperkalaemia or gynaecomastia will be analysed using chi-square test.

To evaluate changes in UACR and eGFR over time (outcome measurement C and H in section 6.2.1) a linear mix model will be applied with adjustment for eGFR and UACR at baseline.

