### **17.3 Justification for selection criteria**

The justification of the second inclusion criteria limiting the age of eligible patients to 75 years is due to the expected prevention potential of the trial. Patient included in the trial must have persistent normoalbuminuria and therefore no sign of diabetic nephropathy at the time of inclusion. The time course of diabetic nephropathy will usually be >10 years from the onset of microalbuminuria to overt kidney disease. Since the aim of the study is to prevent kidney disease (onset of microalbuminuria) we consider it unethical to start preventive medical treatment in patient where the potential onset of disease is after the expected life time.

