5.3.3 Site

15 sites in 10 countries were active recruiting.

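### SAP 6.3.2.2 sets no minimum event count for its site-adjusted Cox model, which is unreliable for sparse renal endpoints, and 6.3.2.1 keeps both randomisation strata out of the primary treatment model

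*SAP*

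**What the plan says.** SAP 6.3.2.2 plans unadjusted and adjusted Cox models for treatment. The adjustment list starts with age, gender and HbA1c and continues: "systolic blood pressure, retinopathy, study site, eGFR and UACR at baseline will be conducted for both primary and secondary endpoints". The same sentence restricts this with "excluding 6.1.2 C, H and J". The adjusted model therefore covers the primary endpoint and secondary outcomes A, B, D, E, F, G, I and K. SAP 5.3.3 reports that "15 sites in 10 countries were active recruiting". The SAP gives no minimum event count and no method for sites without events.

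For the primary treatment comparison, SAP 6.3.2.1 says: "Adjustments in the model will only be performed for eGFR and/or UACR in the case of a significant unbalance in the baseline value", with imbalance judged at p < 0.01. Site cannot enter that model, nor can RAS-blocker use.

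SAP 3.2 names two randomisation factors. Patients are "randomly assigned in a 1:1 ratio to one of the two treatment arms using a block randomization stratified by study center". It adds: "Patients will be stratified in the two treatment arms (1:1) based on whether or not the patients is treated with RAS blocking agents" at screening. The protocol synopsis adjusts the primary-endpoint Cox model for study site, and Protocol 15.6 adds centre at its second adjustment step.

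**The concern.** Three of the covered outcomes look sparse: E (UACR above 300 mg/g), G (eGFR below 30) and possibly I (40% loss of eGFR). Patients enter with normoalbuminuria and eGFR above 45, and follow-up cannot exceed 4.4 years. Protocol 17.3 states: "The time course of diabetic nephropathy will usually be >10 years from the onset of microalbuminuria to overt kidney disease". About 300 patients are randomised. A model with some 22 parameters may then be fitted to a handful of events.

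These results will be shown whatever the primary outcome. SAP 4.1 withholds secondary p-values unless the primary analysis succeeds, but it requires 95% confidence limits for all secondary analyses. An imprecise adjusted hazard ratio for a renal outcome would then stand beside the unadjusted one.

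The handling of site is also uneven. It is left out of the primary treatment model, where about 96 events could support it, and required for endpoints that may not support it. RAS-blocker use, the other stratum, is in neither model.

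**Working it through.** **1. The plan's own figure.** SAP 3.4 gives 24% against 40%, alpha 0.05 (taken as two-sided) and power 0.80. With unpooled variance, n per arm = (1.960 + 0.842)² × (0.24×0.76 + 0.40×0.60) / 0.16² = 7.85 × 0.4224 / 0.0256 = 129.5, which matches the stated 129. Allowing for 10% drop-out, 258/0.9 = 287, so 300 is enough.

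**2. Parameters.** Treatment 1 + seven single-parameter covariates 7 + sites (15 − 1) 14 = 22. This assumes that site is categorical, that retinopathy is binary and that every site randomised patients. Coding is not stated. SAP 6.3.1.3 lists site among continuous variables; one linear site term would give 9 parameters.

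**3. Primary events.** 150×0.24 + 150×0.40 = 96, so 96/22 = 4.4 events per parameter. With 258 patients, 82.6/22 = 3.8.

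**4. Sparse endpoints (assumed counts).** Expected sites without an event, for 15 equal sites = 15 × (14/15)^d.

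| Events d | Events per parameter | Sites with no event |
|---|---|---|
| 5 | 0.23 | 10.6 |
| 10 | 0.45 | 7.5 |
| 20 | 0.91 | 3.8 |
| 30 | 1.36 | 1.9 |

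**5. Simulation.** 300 patients, 15 equal or unequal sites, true HR = ln(0.76)/ln(0.60) = 0.537, 150 runs per cell. SD, mean SE and coverage of the treatment log HR are among finite fits; ranges span equal and unequal sites.

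| Events | Model | SD | Mean SE | Coverage | No finite fit |
|---|---|---|---|---|---|
| about 96 | 22 parameters | 0.22–0.25 | 0.22 | 93–95% | 0 |
| | unadjusted | 0.21–0.25 | 0.21 | 92–96% | 0 |
| about 28 | 22 parameters | 0.47–0.51 | 0.43 | 91–93% | 0 |
| | 8 parameters, no site | 0.43 | 0.41 | 95–97% | 1% |
| | unadjusted | 0.40–0.41 | 0.41 | 97% | 0 |
| about 14 | 22 parameters | 0.73–0.77 | 0.64–0.66 | 94–97% | 3–6% |
| | unadjusted | 0.63–0.64 | 0.60–0.62 | 97–98% | 0 |
| about 7 | 22 parameters | 1.13–1.21 | 0.99–1.00 | 93–97% | 30–33% |
| | 8 parameters, no site | 0.76–0.84 | 0.87–0.89 | 98% | 29–35% |
| | unadjusted | 0.78–0.79 | 0.85–0.88 | 98% | 5–6% |

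An SD from 150 runs carries a relative error of about 1/√300 = 6%. With a true HR of 1 and about 9 events, 23% of full-model runs had no finite fit, against none unadjusted.

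**6. Does stratifying by site cure it?** A separate simulation at about 9 events (HR 0.537) gave:

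- full model: SD 1.05, mean SE 0.91
- same covariates with site as a stratum: SD 0.99, mean SE 0.90
- unadjusted: SD 0.72, mean SE 0.77

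On the hazard-ratio scale, exp(1.96×1.05) = 7.8, so the full-model estimate spreads over a factor of about 7.8 either way. Unadjusted, exp(1.96×0.72) = 4.1. Stratification alone barely changes the picture.

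**7. Arms without events.** The placebo share of events is about 1/(1 + 0.537) = 0.651. The chance of no active-arm event is 0.651⁹ = 2% with 9 events and 0.651⁵ = 12% with 5, so the fallback model also needs a rule for this case.

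**8. Site in the primary model.** With about 100 events and a between-site SD of log hazard of 0.3 and 0.6 (400 runs each), power was 0.81 and 0.85 stratified by site, against 0.86 and 0.81 unadjusted. Simulation error is about √(0.8×0.2/400) = 0.02. Coverage was 93–96% throughout.

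**The case against.** The strongest reply is that little rests on the adjusted model. An unadjusted Cox model is planned for the same endpoints, secondary p-values are conditional on the primary result, and a site-adjusted analysis of the primary endpoint already appears in 6.3.2.2. The documents give no rates for E, G or I, and D, F and K need not be rare. All of this stands and limits the weight of the point. It does not supply an event-count rule.

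Four stronger readings are tempting but not supported.

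- That the model fails for the primary endpoint, at 4.4 events per parameter. In simulation it always fitted, with 93–95% coverage.
- That infinite coefficients for event-free sites wreck the treatment estimate. Such a site drops out of the partial likelihood and the treatment coefficient can stay finite. In a further check at about 9 events, treatment plus site indicators gave an SD of 0.73 against 0.72 unadjusted. The extra spread appeared when site and the seven covariates were fitted together.
- That sparse-endpoint confidence intervals are grossly wrong. Among finite fits coverage stayed at 91–97%. The harm is excess spread, a standard error somewhat too small and fits that fail.
- That omitting site invalidates the primary test. Coverage and power were similar with and without stratification.

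**Conclusion.** The point holds in limited form. For the primary endpoint the adjusted model is acceptable. For endpoints with roughly 30 events or fewer, its treatment hazard ratio is more variable than the unadjusted one and its standard error is somewhat too small. In the range of 7 to 9 events, about a quarter to a third of simulated trials gave no finite estimate. That E, G and possibly I fall in this range is an inference from the entry criteria and follow-up, not a documented rate. The parameter count assumes ordinary categorical coding of 15 sites.

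The omission of both randomisation strata from the primary treatment model is a departure from the design, and for site also from the protocol's own models. It is not a threat to validity. The change is worth making, but no main conclusion of the trial depends on it.

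**What to change.** 1. In SAP 6.3.2.1 and 6.3.2.2, stratify the Cox models by centre, with a stated rule for pooling very small sites, and include RAS-blocker use at screening as a stratum or covariate. This uses no site coefficients.
2. In SAP 6.3.2.2, set a minimum event count for the covariate-adjusted model. Below it, report the treatment-only model stratified by the randomisation factors, with event counts by arm, and use Firth-penalised estimates when an arm has no events.

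The second item repairs the sparse endpoints. The number is a judgement. Ten events per parameter would require 80 events for 8 parameters, which is stricter than the simulations call for. At about 28 events the 8-parameter model without site had 95–97% coverage and 1% failed fits, so a threshold near 30 would be defensible. The stratified version of that model was not simulated at that count.

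The cost is SAP wording, fewer adjusted results for rare outcomes and a small loss of information from very small sites. The change should be dated before unblinding.

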### 7.1 Inclusion Criteria

- 1) Written informed consent must be provided before participation. Patient information and consent form must be approved by relevant independent EC. Specifically, all participating patients will be asked to give informed consent for long-term follow-up
- 2) Male or female patients  $\geq 18$  years and  $< 75$  years of age at Screening visit
- 3) Type 2 DM (WHO criteria)
- 4) Persistent normoalbuminuria (at least 2 of 3 UACR  $< 30$  mg/g samples from "run in"-period)
- 5) eGFR  $> 45$  ml/min/1.73m^2 at Screening visit
- 6) The patient must be willing and able to comply with the protocol for the duration of the study
- 7) Female without child-bearing potential at the screening visit. Defined as one or more of following:
  - 7.1) Female patients  $\geq 50$  years of age at the day of inclusion, who have been postmenopausal for at least 1 year
  - 7.2) Female patients  $< 50$  years of age at the day of inclusion, who have been postmenopausal for at least 1 year and serum FSH levels  $> 40$  mIU/mL as well as serum estrogen levels  $< 30$  pg/ml or a negative estrogen test.
  - 7.3) 6 weeks after surgical sterilization by bilateral tubal ligation or bilateral ovariectomy with or without hysterectomy.  
OR a negative urine pregnancy test at the Screening visit AND one or more of following:
  - 7.4) Correct use of reliable contraception methods. This includes one or more of the following: hormonal contraceptive (such as injection, transdermal patch, implant, cervical ring or oral) or an intrauterine device (IUD) OR correct use of double barrier with one of the following: barrier methods (diaphragm, cervical cap, Lea contraceptive, femidom or condom) AND in combination with a spermicide.
  - 7.5) General sexual abstinence from the time of screening/ during the study until a minimum of 30 days after the last administration of study medication if this is already established as the patient's preferred and usual lifestyle.
  - 7.6) Having only female sexual partners.
  - 7.7) Sexual relationship with sterile male partners only.

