## 14 RISK ASSESSMENT AND WITHDRAWAL RULES

### 14.1 Potential risks

For the patients, sample collection bare minuscule risks of infection at the venipuncture site.

Patients in the intervention groups will be randomized to placebo or spironolactone on top of standard treatment with the potential common site effects like fatigue, hyperkalemia, hyponatremia, gynecomastia and disorder of menstruation (see section 11.3)

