## 15.8 Analysis of safety endpoints

The exposure of study treatment will be characterized by number of administrations and the cumulative dose for both treatment groups.

AEs will be coded using the MedDRA via MARVIN.

An overview of all eCRF-documented AEs will be prepared. For all these categories of AEs (see section 13.3) separate frequency tables will be provided presenting the AEs by MedDRA preferred terms, SOC and treatment groups.

In addition AEs leading to death and AEs leading to discontinuation of study medication will be summarized for the two treatment groups.

Safety laboratory results will be classified by grade according to CTCAE version 4.0. The worst on-study grades after the first dose of study medication will be summarized. Only patients with post-baseline laboratory values will be included in these analyses. Furthermore, summary statis-

tics (mean, median, SD, SEM, range) will be calculated for the laboratory values at the various visits and for the changes from baseline. Baseline values are defined as the last available value prior to start of study treatment.

Corresponding descriptive summaries will be generated for vital signs.

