3.4 Sample size

The expected relative proportions of diabetes type 2 patients developing microalbuminuria in our study population are: 24% in patients at high-risk for diabetic nephropathy in the treatment group, 40% in those patients at high-risk for diabetic nephropathy in the placebo group and 8.5% in those therapy-naive patients at low-risk for diabetic nephropathy. Using the sample size formula for two proportions test ($\alpha= 0.05$ $\beta=0.80$), randomized (1:1), $n=129$ in each arm of the intervention group are required. To account for an expected drop-out rate of 10 %, we plan to include 300 participants in the intervention part of the study.

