4 STATISTICAL PRINCIPALS

4.1 Confidence limits and significance level

Any p-value below 0.05 will be considered statistically significant. A p-value will be calculated for the primary analysis. P-values for the secondary analyses will only be calculated if the primary analysis yields a p-value below 0.05. For all primary and secondary analyses 95 % confidence limits will be calculated.

Continuous values fulfilling terms of normal distribution will be displayed as mean values and 95 % confidence limits of the mean. Variables not fulfilling terms of normal distribution will be displayed as median and inter quartile range from p25 to p75.

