4.3.3 Intention to treat cohort

All participants with a valid proteomic score with a high-risk pattern who was provided with study medication

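### SAP 6.3.2.2 sets no male denominator for gynaecomastia, so the reported absolute risk shrinks with the share of women; hyponatraemia has no formal between-arm test

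*SAP*

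**What the plan says.** SAP 6.1.2 lists safety as outcome J (adverse events, serious adverse events, and events leading to death, discontinuation or withdrawal). For its analysis, SAP 6.3.2.2 says that "only AE/SAE with the term hypotension, hyperkalaemia or gynaecomastia will be analysed using chi-square test".

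That paragraph falls under SAP 6.3.2, whose heading names the intention-to-treat cohort. SAP 4.3.3 defines the cohort as "All participants with a valid proteomic score with a high-risk pattern who was provided with study medication". Protocol 7.1 admits "Male or female patients", and neither document restricts any safety analysis by sex.

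Protocol 14.1 lists "potential common site effects like fatigue, hyperkalemia, hyponatremia, gynecomastia and disorder of menstruation". Hyponatraemia is also an exclusion criterion (7.2). Sodium is measured at every visit (10.8) and is named beside potassium among the laboratory abnormalities to be entered in the eCRF (13.3.1.1). Potassium has a tested adverse-event term and a threshold outcome of its own (SAP 6.1.2 K). Sodium has neither.

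Protocol 15.8 promises that "separate frequency tables will be provided presenting the AEs by MedDRA preferred terms, SOC and treatment groups". It adds CTCAE-graded laboratory results and summary statistics by visit and for change from baseline.

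**The concern.** Gynaecomastia is a condition of men. A whole-cohort proportion includes people who cannot have the event, so it is not the risk that a man considering treatment would face. Gynaecomastia is the first side effect described in protocol 11.3. The treatment is preventive, given to people who still have normal albumin excretion, so the absolute size of a harm carries weight. SAP 6.3.2.2 also reports benefit as a number needed to treat. A diluted harm rate beside it would make the balance look better than it is for men.

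Separately, the SAP singles out three terms for testing and leaves out one that the protocol treats as a safety concern and measures throughout. A sodium imbalance would appear only in descriptive tables that the SAP does not mention.

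**Working it through.** **Inputs from the documents.** SAP 3.4 states that "we plan to include 300 participants in the intervention part of the study", randomised 1:1, so 150 per arm. The size behind it, 129 per arm for 24% against 40%, reproduces with the unpooled two-proportion formula: (1.960 + 0.842)² × (0.24 × 0.76 + 0.40 × 0.60) / 0.16² = 129.5. It has no bearing on safety; only the 150 per arm is used below. The documents give no expected gynaecomastia rate.

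**Assumptions.** The share of men, m, is not in the documents and is varied over 50-80%. Male risks are illustrative. Women have no events, and the sexes are balanced between arms.

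**Step 1, absolute risk.** Reported risk = m × male risk. The risk difference scales in the same way.
- Male risk 8%: 0.55 × 8% = 4.4%; 0.70 × 8% = 5.6%.
- Male risk 10%: 0.50 × 10% = 5%; 0.80 × 10% = 8%.
- With no placebo events, the number needed to harm implied by 8% is 1/0.08 = 12.5 in men, against 1/0.056 = 17.9 to 1/0.044 = 22.7 in the whole cohort. The SAP does not promise this figure; it only shows the scale.

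**Step 2, relative risk.** (m × active risk) / (m × placebo risk): m cancels, so there is no change.

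**Step 3, the test.** Take m = 60% (90 men per arm) and male risks of 10% and 1%, that is, expected counts of 9 and 0.9. Pearson chi-square without correction:

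| Denominator | Active | Placebo | Risk difference | Pooled risk | Chi-square | p | Power |
|---|---|---|---|---|---|---|---|
| Men, 90 per arm | 10.0% | 1.0% | 9.0 points | 5.5% | 0.09² / (0.055 × 0.945 × 2/90) = 7.01 | 0.0081 | 75.9% |
| All, 150 per arm | 6.0% | 0.6% | 5.4 points | 3.3% | 0.054² / (0.033 × 0.967 × 2/150) = 6.85 | 0.0088 | 74.7% |

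The two statistics differ by the factor (1 − 0.033)/(1 − 0.055) = 1.02. Over 50-80% men, with male risks of 5-10% on active treatment and 1-2% on placebo, the largest loss of power is about 1.5 points (68.0% to 66.5%).

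**Step 4, hyponatraemia.** Set the SAP's between-arm analyses beside the protocol's named risks. Hyperkalaemia has a chi-square test under J and a Cox model as outcome K. Renal function has Cox models for F (eGFR below 60), G (below 30) and I (40% reduction), because SAP 6.3.2.2 excludes only C, H and J from those models; H (eGFR slope) has a mixed model. Hyponatraemia has no test. It has the descriptive tables of protocol 15.8 and the by-group summary of laboratory abnormalities in protocol 5.6.

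**The case against.** The strongest reply has four parts.

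First, the SAP names no denominator, so counting women is an inference. That is fair. It is the default reading of the section and cohort definition, not an explicit instruction, which is why a clarification is enough.

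Second, what the section specifies is a test, and the test is nearly unaffected. Step 3 confirms this. A reader might infer that including women hides a real difference; the arithmetic does not support that. What remains is the rate and risk difference that will be printed beside the p-value. Sex-specific counts would let a reader undo the dilution, but the SAP does not promise them.

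Third, testing a few prespecified terms and describing the rest is ordinary practice, and the restriction governs which terms get a chi-square test, not which are tabulated. This also stands. A reader might infer that hyponatraemia and kidney events are never compared. They are: protocol 15.8 tabulates eCRF-documented events by arm, and outcomes F to I compare renal function formally. The case for adding hyponatraemia is that the protocol names it as a common risk and already collects the data; not every listed side effect needs a test.

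Fourth, a male denominator would still not give the true male risk if events are not recorded. Protocol 13.3.1.1 limits eCRF events to listed categories, and non-serious gynaecomastia that does not lead to discontinuation is not clearly among them. This is a real limit that the report should state; it does not justify the wrong denominator.

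**Conclusion.** The point holds in a limited form. As written, the plan would by default report a gynaecomastia risk and risk difference multiplied by the share of men: 4.4-5.6% for an 8% male risk if 55-70% are men. The male share, the male risk and the absence of events in women are assumptions; the direction and the scaling are not sensitive to them. The relative risk is unchanged and the p-value almost unchanged. Hyponatraemia lacks a formal between-arm comparison but is covered descriptively.

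A reader might also infer that the chi-square test is unreliable here. The documents give no expected safety counts from which to show that, so it is not part of this point. Nothing here touches the primary result; the consequence is for how harms are presented beside benefit.

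**What to change.** In SAP 6.3.2.2:
- Define the gynaecomastia analysis in male participants of the intention-to-treat cohort. Report events and number of men by arm, with the risk difference and 95% CI. SAP 4.1 already commits to 95% limits for secondary analyses without naming the measure.
- Add hyponatraemia to the between-arm safety comparisons, using the adverse-event term and the sodium values already collected. State the laboratory definition before unblinding; the CTCAE grading in protocol 15.8 is already planned.
- State that the adverse-event and laboratory tables of protocol 15.8, by arm, still apply.
- Report the gynaecomastia rate with the caveat that the eCRF list in protocol 13.3.1.1 does not clearly capture non-serious cases that do not lead to discontinuation.
- Correct the cross-reference: the section cites outcome J at 6.2.1, but it is in 6.1.2.

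The cost is a few lines of SAP text and a few tables from data already collected. The reported gynaecomastia rate will be higher, because it will be the rate in men.
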